### 16.2 Procedures for orderly termination/subject withdrawal

1. PI, Study Physician, or individual designated in the Delegation of Authority will contact the study participant and their family.
  - a. If the participant initiates the withdrawal, reasons will be documented and if applicable, intervention or plans for follow-up will made.
  - b. If the study team terminates the subject's participation in the study, study personnel will clearly explain the reasons for removal from the study and if applicable,

discuss next steps for necessary interventions or plan for follow-up care (e.g titration schedule for discontinuing study drug, etc).

2. If applicable, adverse events related to withdrawal will be promptly reported to the IRB per CM Policy 5.11 “Reportable Events”. Adverse events will continue to be followed until resolution.
3. Study personnel will complete end-of-study and withdrawal documentation in the subject binder.
4. All previously collected samples and data, regardless of whether participant completed the research study in its entirety, will be saved for data analysis.
5. Transfer of care procedures from the study physician to the participant’s primary care provider will take place in accordance with those outlined in section 11.6 for participants completing the study in its entirety.

## 17.0 Risks to Subjects

- Confidentiality Risk: There is a risk of loss of confidentiality. Confidentiality will be protected to the greatest extent possible. There is also a risk of loss of confidentiality when using the internet. This is especially pertinent when filling out questionnaires using a web interface. The study team will make every effort to protect the participant’s confidentiality such that this risk is minimal.
- Blood Draw: Risks of drawing blood include discomfort and/or bruising. A needlestick can be greater than minimal risk. However, numbing spray and topical lidocaine can be provided to minimize pain associated with needle sticks. In addition, the study team will inquire about needlestick fears and comfort techniques prior to the first needlestick.
- Allergic reaction: It is possible to have an allergic reaction to atomoxetine. Currently, there is no way to predict whether an individual will have an allergic reaction to atomoxetine *a priori*. However, the percentage of individuals experiencing allergic reaction is low. The first dose of atomoxetine will be administered

to the participant in the PCRU. Medications and procedures are in place should a participant have an allergic anaphylactic reaction to atomoxetine.

- Genetic Risks: The unauthorized disclosure of genetic information may have an impact on a participant's employability, insurability, immigration status, paternity suits, or social reputation. These risks include the chance of discrimination. The study team will make every effort to protect the participant's genetic such that this risk is minimal. Additionally, the genes investigated in the study have thus far only been associated with drug pharmacokinetics and pharmacodynamics. The risk of discrimination with this type of genetic information is lower compared to genes linked to predisposition of disease.
- Side Effects Risks: Participants may experience side effects of atomoxetine related to the way the medication is dosed. Typical side effects include increased heart rate, headache, stomach upset, nausea, sleepiness, and emotional lability. In addition, there are reports of suicidal ideation with atomoxetine use. The level of risk is variable given that the severity of side effects can be different among participants.
- Psychological Risks: There may be psychological risks associated with answering questions about the participant's mood and behaviors at home and at school. The level of risk in answering psychological questionnaires would be equal to an individual seeing care for ADHD and comorbidities associated with ADHD, as many of these questionnaires are used to assess symptoms and improvement. We therefore expect the psychological risks to pose no increase in psychological risks over baseline.

## 18.0 Potential Benefits to Subjects

- Personalized Medication Dosing: Participants will receive more personalized dosing of atomoxetine therapy through participation in study.

- **Genetic Information:** Participants will have genetic information returned to them (as it is related to duration of study visits) and will be given information about the GOLDILOKs Clinic at Children Mercy's Hospital where they can learn about the impact that their unique genetic information has on the way their body processes ATX and numerous other medications. As mentioned previously in section 14.0, it will be explained to families that genetic testing results obtained as part of the study cannot be used by GOLDILOKs Clinic for interpretation, but rather, that the testing will need to be repeated in a CLIA-certified lab. If the participant and/or family would like to be seen in GOLDILOKs Clinic and repeat genetic testing, these services will not be paid for by the study and will be the responsibility of the participant/family.

## 19.0 Investigator Assessment of Risk/Benefits Ratio

Select as applicable:	Pediatric Risk Category:	
	Category 1	Research not involving greater than minimal risk (45 CFR §46.404 and 21 CFR §50.51)
x	Category 2	Research involving greater than minimal risk but presenting the prospect of direct benefit to the individual subjects. (45 CFR §46.405 and 21 CFR §50.52)
	Category 3	Research involving greater than minimal risk and no prospect of direct benefit to individual subjects, but likely to yield generalizable knowledge about the subject's disorder or condition. (45 CFR §46.406 and 21 CFR §50.53)
	Category 4	Research not otherwise approvable which presents an opportunity to understand, prevent, or alleviate a serious problem affecting the health or welfare of children. (45 CFR §46.407 and 21 CFR §50.54)
Select if applicable:	Adult Risk Category:	
	Not Greater than Minimal Risk	
x	Greater than Minimal Risk	

## 20.0 Data Management

### 20.1 Data Analysis Plan

#### Population to be Analyzed:

- The pharmacokinetic population will consist of all participants with sufficient plasma concentrations for calculation of all pharmacokinetic parameters.
- The pharmacodynamic population will comprise of all patients with sufficient DHPG plasma concentrations, adequate data from pupil dilation and eye-tracking measurements, and cardiovascular measures (heart rate and blood pressure). Additional metabolites analyzed via metabolomics platform will also be analyzed (as discussed below).
- All participants who meet criteria for determination of both pharmacokinetic and pharmacodynamic parameters and have at least partially completed the study will be evaluated for pharmacodynamic linked clinical outcomes analysis. A partial completion is any participant where at least Research Visit 1, Research Visit 2, Research Visit 3, Intake Visit with Physician, and 6-week Visit with Study Physician have been completed. Clinical outcomes will be analyzed in four ways:
  - Response: responder vs. non-responder
  - Toxicity: tolerant vs. non-tolerant
  - Adherence: low, medium, and high
  - Adverse event reporting
- In addition, all participants for which demographic and background characteristics and concomitant medication history were collected will be analyzed.
- All completed and returned U54 Study Booklet questionnaires and surveys will be used to assess the effectiveness of the U54 Study Booklet in study comprehension. Feedback from the survey will be compiled for analysis.

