#### Pharmacokinetics:

Estimation of the pharmacokinetic parameters and generation of the statistical analyses on the PK parameters will be performed by The Division of Clinical Pharmacology Toxicology & Therapeutic Innovation at the Children's Mercy Hospital, Kansas City, MO. Pharmacokinetic analyses will be conducted using Kinetica™ version 5.0 (ThermeElectron, Philadelphia, PA). Plasma ATX concentration versus time data will be curve fit using a peeling algorithm to generate initial polyexponential parameter estimates. Final parameter estimates will be determined from an iterative, nonlinear weighted least squares regression algorithm with reciprocal ( $1/y^2_{\text{calc}}$ ) weighting. Model-dependent pharmacokinetic parameters will be calculated from final polyexponential parameter estimates. Final model selection will be performed by evaluating the

goodness-of-fit criteria including; the objective function, Akaike & Schwartz criteria, standard deviations and coefficients of variation for the polyexponential parameters estimates and the correlation matrix detailing the degree of interdependence between the parameter estimates for each model. In the event that an insufficient number of post-peak ATX plasma concentration time points are available, a model-independent approach will be used and parameters of interest calculated using standard techniques. Specifically,  $C_{max}$  and  $T_{max}$  will be obtained by direct examination of the plasma concentration versus time profile. The area under the plasma concentration versus time curve during the sampling period ( $AUC_{0-n}$ ) will be calculated using the mixed log-linear rule and extrapolation of the AUC to infinity ( $AUC_{0-\infty}$ ) calculated by summation of  $AUC_{0-n} + Cp_n/\lambda_z$ , where  $Cp_n$  represents the final plasma concentration predicted from the fitted apparent terminal elimination phase and  $\lambda_z$  is the apparent terminal elimination rate constant. Model-independent pharmacokinetic parameters will then be calculated using standard (i.e., statistical moment theory) techniques. ATX metabolites *N*-desmethylatomoxetine (NDM-ATX), 4-hydroxyatomoxetine (4-OH-ATX) and hydroxyl-2-carboxylatomoxetine (OH-2-COOH-ATX) pharmacokinetics will be evaluated in a fashion analogous to that described for the parent compound.

The following PK parameters will be derived by non-compartmental analysis from plasma concentration data following a single dose study drug administration:

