$C_{max}$	Peak plasma concentration determined from the observed data
$T_{max}$	Time to observed maximum drug concentration
$AUC_{0-\tau}$	Area under the plasma concentration versus time curve, determined by log-linear trapezoidal estimation, to the 12 or 24 hour time point (depending on CYP2D6 AS designated study design).
$AUC_{0-\infty}$	Area under the concentration versus time curve to infinity, determined by log-linear trapezoidal estimation $AUC_{0-\tau} + C_{\tau}/k$ Where $k$ is the elimination rate constant defined as the negative slope following maximum concentration determined by least squares regression from terminal phase data.
$T_{1/2}$	Terminal half-life determined by quotient $0.693/k$
$CL/F$	Oral clearance determined by quotient dose/ $AUC_{0-\infty}$
$Vd/F$	Terminal phase volume of distribution determined by Dose/ $k \cdot AUC_{0-\infty}$

fm	Fraction of drug metabolized through different pathways of biotransformation
----	--

The following PK parameters will be derived by non-compartmental analysis from plasma concentration data following chronic dosing to steady-state of study drug:

$C_{max,ss}$	Peak plasma concentration determined from the observed data at steady-state
$T_{max, ss}$	Time to observed maximum drug concentration at steady-state
$AUC_{0-\tau,ss}$	Area under the plasma concentration versus time curve, determined by log-linear trapezoidal estimation, to the 12 or 24 hour time point (depending on CYP2D6 AS designated study design).
$T_{1/2}$	Terminal half-life determined by quotient $0.693/k$
$CL/F_{ss}$	Oral clearance determined by quotient dose/ $AUC_{0-\infty}$
$Vd/F_{ss}$	Terminal phase volume of distribution determined by Dose/ $k \cdot AUC_{0-\infty}$

iGO-PK Model Update: The current iGO-PK Model (Version 1.0) uses ATX pharmacokinetic data from 24 pediatric participants (Brown et al., 2016). Since the building of Version 1.0, more ATX pharmacokinetic data has been collected from studies conducted at Children's Mercy Hospital (IRB# 16010069) and this current study. The data will be used to update and refine the iGO-PK model when it has been determined that sufficient new data has been collected. This determination will be made by the Principal Investigators and other Co-Investigators.

Pharmacodynamics:

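### Entry to the PD-linked clinical-outcome analysis requires every PK parameter, so a child with an observed Cmax but no terminal slope may be left out of outcomes that need no slope

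*Combined protocol and SAP*

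**What the plan says.** Section 20.1, under Population to be Analyzed, sets the entry rule for the PK set: "The pharmacokinetic population will consist of all participants with sufficient plasma concentrations for calculation of all pharmacokinetic parameters". It does not define how many concentrations are sufficient, or at which visit. Two bullets later comes the entry rule for the PD-linked clinical-outcome analysis: "All participants who meet criteria for determination of both pharmacokinetic and pharmacodynamic parameters and have at least partially completed the study will be evaluated". Under that bullet the plan says "Clinical outcomes will be analyzed in four ways" and lists response, toxicity, adherence and adverse event reporting.

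The Pharmacokinetics part of Section 20.1 lists the parameters. The elimination rate constant is "determined by least squares regression from terminal phase data". A shortage of samples is foreseen: "In the event that an insufficient number of post-peak ATX plasma concentration time points are available, a model-independent approach will be used". Under that approach Cmax and Tmax "will be obtained by direct examination of the plasma concentration versus time profile", while AUC to infinity is still the observed area plus the last predicted concentration divided by the terminal rate constant.

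Section 8.2 counts toward the target of 120 any child who has finished Research Visits 1 to 3, the Intake Visit and the 6-Week Visit, on the ground that such data serve the study aims. It sets no PK condition.

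**The concern.** The word that matters is all. Read as written, one parameter that cannot be calculated takes a child out of the PK set, and with it out of the PD-linked analysis of four clinical outcomes, none of which is derived from a terminal slope. The exposure goal in Sections 3.3 and 5.1 is a peak concentration, so a child whose Cmax,ss has been observed already carries the information needed to judge exposure control.

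Two things are at stake. First, avoidable exclusion: children counted as completers under Section 8.2 may be missing from the analysis that the count was meant to serve. Second, possible selection: whether a slope can be estimated depends on the time of the peak, on missed draws and on the sampling schedule. Exclusion could therefore be related to pharmacokinetics in a study that aims to separate exposure from effects at the drug target.

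**Working it through.** **1. Which parameters need the slope k (tables in Section 20.1)**

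- From observed data: Cmax, Tmax, AUC over the sampled interval.
- Through k: AUC0-∞ = AUC0-τ + Cτ/k; T1/2 = 0.693/k; CL/F = dose/AUC0-∞; Vd/F = dose/(k·AUC0-∞).
- The steady-state table again lists T1/2, CL/F and Vd/F.
- fm is listed without a formula.

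**2. Which analyses need it**

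- Responder against non-responder comparison of DHPG change, and the difference in SLC6A2 proportions (Sections 20.1 and 20.2): no slope.
- Plots of pupillometry against AUC0-∞: slope needed.
- Imax and IC50: need ATX concentration-time data, and so some PK condition.

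**3. Does the schedule supply a slope?** Study Design 2 draws fall at 0.5, 0.75, 1, 1.5, 2, 3, 4, 6, 8, 10 and 12 h. Draws left after the highest observed value:

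| Peak at | 2 h | 3 h | 4 h | 6 h | 8 h | 10 h |
|---|---|---|---|---|---|---|
| Later draws | 6 | 5 | 4 | 3 | 2 | 1 |

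The documents give no half-lives, so I assume one-compartment kinetics with absorption rate 0.7 to 3 per h and half-life 4 to 8 h. The latest peak comes from 0.7 per h with 8 h:

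- k = 0.693/8 = 0.0866 per h
- Tmax = ln(0.7/0.0866)/(0.7 − 0.0866) ≈ 3.4 h

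The highest sampled value is then at 3 h, with five later draws. A complete profile therefore gives a slope throughout this range.

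An incomplete one may not. With a peak at 3 h and the line lost after the 6 h draw, two post-peak points remain (4 and 6 h), which leaves a regression line no residual degree of freedom. In Study Design 3 with a 6 h gap, the first-dose profile has three later draws after a peak at 2 h and two after a peak at 3 h. The second dose is followed to 16 h, so it may still provide a slope.

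**4. Power.** Inputs from Section 20.2: 30% responders, one-sided α = 0.05, power 80%, N = 96 = 120 × 0.80. Formula: d = (1.645 + 0.842) × √(1/(0.3N) + 1/(0.7N)).

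- N = 96: 2.487 × √(1/28.8 + 1/67.2) = 0.554 SD; with the noncentral t distribution 0.557 SD (plan: 0.6).
- N = 120: 2.487 × √(1/36 + 1/84) = 0.495 SD; noncentral t 0.498 SD (plan: 0.5).

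The plan's figures reproduce after rounding. The share of children without all parameters is not given, so the losses below are assumptions (noncentral t):

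| Loss | N | Detectable difference | Power for 0.6 SD |
|---|---|---|---|
| none, from 96 | 96 | 0.557 SD | 85.0% |
| 10% of 96 | 86 | 0.589 SD | 81.3% |
| 20% of 96 | 77 | 0.625 SD | 77.1% |
| 10% of 120 | 108 | 0.527 SD | 88.2% |
| 20% of 120 | 96 | 0.557 SD | 85.0% |
| 30% of 120 | 84 | 0.598 SD | 80.2% |

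**The case against.** The strongest case on the other side is that the rule will exclude few children and that the plan already provides for them. Several parts of that case stand.

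- A reader might infer that, by the plan's own account, some children cannot supply all parameters. The text does not go so far. The shortage is conditional and concerns the curve fit. The fallback needs fewer points and still aims at AUC to infinity. It rescues some profiles, though not those with too few post-peak points for any slope.
- A reader might infer that slow decline over a 12-hour window leads to exclusion because much of the area is extrapolated. The rule asks whether a parameter can be calculated, and the plan sets no limit on extrapolation.
- A reader might infer that those lost are the more highly exposed. The documents do not support one direction. At fixed dose and clearance slower absorption lowers Cmax (about 22% lower at 0.7 than at 3 per h with an assumed half-life of 5 h), while slower elimination raises it. Children with an activity score below 1 or two reduced-function alleles are in Study Design 1, sampled to 72 h at Research Visit 2 and 24 h later.
- A reader might infer that response data are dropped everywhere. The condition is attached to the PD-linked analysis. The text on baseline predictors and SLC6A2 genotype does not name its analysis set.
- Some PK condition is reasonable for Imax, IC50 and the AUC0-∞ regressions.

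None of this explains why a missing half-life or volume of distribution should decide whether a child's response or adverse events enter the PD-linked analysis.

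**Conclusion.** The point holds in a limited form. The entry rule is stricter than the PD-linked outcomes require, its threshold is undefined, and it does not match the visit-based count in Section 8.2. The children exposed to it are those with a late peak, a lost line or missed late draws whose Cmax was nevertheless observed.

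The size is unknown and may be small. If the loss falls within the 20% already allowed between 120 and 96, the stated power is unaffected. Only a loss on top of that allowance matters: at an assumed further 20%, the detectable difference is 0.625 SD and power for 0.6 SD is 77.1%. Selection related to pharmacokinetics is possible, but neither its direction nor its extent can be derived from the documents. This is a low-cost improvement to the analysis sets and does not show that the planned analysis fails.

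**What to change.** In Section 20.1, Population to be Analyzed:

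1. Define PK evaluability for the clinical-outcome analysis as an observed Cmax,ss at Research Visit 3, and say what counts as observed (for example, a highest value followed by at least one lower one). Partial completion already requires that visit.
2. Do not add an AUC condition. The sampled interval is 12 h, 24 h or a split two-dose profile depending on study design, so it is not comparable between children.
3. Use parameter-specific sets for AUC, AUC0-∞, T1/2, CL/F, Vd/F, fm and the fitted PK/PD parameters. A child missing one is left out of the analysis of that parameter only.
4. State which set each response and SLC6A2 test in Sections 20.1 and 20.2 uses.
5. Report how many children counted under Section 8.2 are absent from each set, with reasons.

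The cost is SAP wording, with no new data collection. The drawback is that denominators will differ between parameters and must be shown in each table.

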### **8.2 Target Participants**

The research proposal targets 160 participants who are expected to be enrolled and screened. The target number of subjects needed to complete research procedures is 120. Participants who complete at least Research Visits 1-3, the Intake Visit, and the 6-Week Visit with the Study Physician will be considered to have "partially completed" the study. Completion of these visits will include obtaining baseline measurements, confirmation of eligibility, single and steady-state PK and PD measurements, and at least one post-treatment clinical response assessment. Since data from these participants will meet the study aims, those who partially complete the study will be counted toward the 120.

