## 20.2 Sample Size Determination

We hypothesize that there are at least two discrete ATX response phenotypes groups and additionally that these groups may be distinguished by differences in pharmacodynamic markers, and/or baseline patient characteristics. We will use two-sample *t*-tests (if transformed data are approximately Gaussian) or appropriate non-parametric alternatives to test for group differences in baseline and maximal change in DHPG, and a difference in proportions test to assess association between response group and SLC6A2 genotype. To estimate power for these tests we assumed 20% attrition and simulated data for 96 patients. For a 30% response rate among study completers (a conservative estimate),  $\alpha = 0.05$ , and power = 80%, a mean difference of 0.6 SDs between responders and non-responders (eg, on DHPG) was detectable using a one-sided *t*-test. With 120 patients (zero attrition) a 0.5 SD difference was detectable. Depending on the rate and nature of attrition and missing data we will consider non-response weighting or data imputation to reduce estimation bias and improve power. We assessed power for the difference in proportions test based on a 45% probability of a given patient having at least one SLC6A2 lower expression “T” allele (*i.e.*, frequency of SLC6A2 -3081 AT and TT genotypes ~45% based on a minor T allele frequency of 0.061

([http://useast.ensembl.org/Homo\\_sapiens/Variation/Population?db=core;g=ENS G00000103546;r=16:55655604-55706192;v=rs28386840;vdb=variation;vf=109832868](http://useast.ensembl.org/Homo_sapiens/Variation/Population?db=core;g=ENS G00000103546;r=16:55655604-55706192;v=rs28386840;vdb=variation;vf=109832868))).

Assuming attrition of 20% and a response rate of 30%, power was 81% to detect a 0.23 difference in allele frequency between responders and non-responders using a one-sided test. With 120 patients a 0.20 difference was detectable with 80% power.

While these analyses are central to our hypothesis, we recognize that other plasma metabolites or genetic differences may contribute to varying drug response. A target metabolite panel will be assayed in each participant and statistical analyses of these will be analogous to DHPG. A panel of genetic variants will also be analyzed for contribution to variable drug pharmacokinetics, pharmacodynamics, and clinical response in the same manner as the SLC6A2 variant described above.

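### The pharmacodynamic population requires adequate DHPG, pupillometry and cardiovascular data jointly, so read literally it drops children with complete DHPG data from a comparison that uses DHPG alone

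*Combined protocol and SAP*

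**What the plan says.** Section 20.1 (Population to be Analyzed) sets out the populations as a short list.

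- **Pharmacokinetic population:** "all participants with sufficient plasma concentrations for calculation of all pharmacokinetic parameters".
- **Pharmacodynamic population:** patients with "sufficient DHPG plasma concentrations, adequate data from pupil dilation and eye-tracking measurements, and cardiovascular measures (heart rate and blood pressure"). There is no 'or', no wording that ties the requirement to the marker being analysed, and no threshold for what counts as sufficient or adequate.
- **Clinical outcomes:** the entry rule is "All participants who meet criteria for determination of both pharmacokinetic and pharmacodynamic parameters and have at least partially completed the study". As for scope, the bullet says that these children "will be evaluated for pharmacodynamic linked clinical outcomes analysis". Response, toxicity, adherence and adverse event reporting are listed under this bullet. No other analysis set is defined for these four outcomes.

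Other parts of the plan treat the markers separately. Hypothesis 1 (section 2.2) names DHPG curves and pupil size as two outcomes. The Clinical Outcomes text in section 20.1 compares percent decrease in DHPG between response groups with a two-sample test, and it also allows MANOVA across several pharmacodynamic measures. Section 20.2 states its power in DHPG terms: with 96 patients, "a mean difference of 0.6 SDs between responders and non-responders (eg, on DHPG) was detectable using a one-sided" t-test at 80% power.

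Section 8.2 counts participants by visits completed, not by whether their marker data are usable: "Since data from these participants will meet the study aims, those who partially complete the study will be counted toward the 120".

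**The concern.** One joint definition cannot serve both single-marker and multi-marker analyses. MANOVA needs every marker on every child. The two-sample DHPG test needs only DHPG and the response classification. Applied as written, the definition makes eligibility for the DHPG test depend on whether a child could complete an eye-tracking task.

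Two things are at stake. The first is sample size in the comparison that the power statement is built on. The second is selection. The task in section 4.1 uses a chin rest, a fixation cross and 162 recorded trials, in children from age 6 with ADHD. Failing it need not be unrelated to the child's condition, so conditioning the DHPG comparison on passing it could select a non-representative group. The documents contain nothing that would give the direction or size of that effect.

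There is also a practical issue. If the intended reading is marker by marker, the text does not say so, and the choice of set could then be made after the data are seen.

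**Working it through.** **Inputs from the documents.** Section 20.2: N = 96 after 20% attrition from 120; 30% responders; α = 0.05 one-sided; 80% power; stated detectable differences 0.6 SD (N = 96) and 0.5 SD (N = 120).

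**Input not in the documents.** The proportion of children with unusable pupillometry. I assume 10% and 20% as a range.

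**Formula.** Detectable difference = (z₀.₉₅ + z₀.₈₀) × √(1/n₁ + 1/n₂) = 2.487 × √(1/n₁ + 1/n₂), then refined with the exact noncentral t.

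**Step 1: reproduce the plan's figures.**

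- N = 96, split 29/67: 2.487 × √(1/29 + 1/67) = 2.487 × 0.2223 = 0.553; exact t gives 0.557. This rounds to the stated 0.6.
- N = 120, split 36/84: 2.487 × 0.1992 = 0.495; exact t gives 0.498. This rounds to the stated 0.5.

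Both figures reproduce. Because 0.557 was rounded up, power at exactly 0.6 SD with 96 children is 85%, so there is some slack.

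**Step 2: remove children for unusable pupillometry only (exact t, one-sided).**

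| Assumed failure | N | Split | Power at 0.6 SD | Difference detectable at 80% |
|---|---|---|---|---|
| 0% | 96 | 29/67 | 85% | 0.557 SD |
| 10% | 96 × 0.9 ≈ 86 | 26/60 | 81% | 0.589 SD |
| 20% | 96 × 0.8 ≈ 77 | 23/54 | 77% | 0.625 SD |

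Power at 0.6 SD stays at 80% down to about N = 84 (80.2%); at N = 82 it is 79.8%. The slack therefore absorbs a loss of about 12% from 96 (12/96 = 12.5%).

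**Step 3: what the joint rule costs relative to a DHPG-only set.** The rule applies to three measures, so the loss depends on how failures overlap. Suppose, as an assumption, that 10% fail each measure.

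- Failures independent: 96 × 0.9³ = 69.98. With 69 children (21/48), power at 0.6 SD is 73%. A DHPG-only set keeps 86 and has 81%.
- The same children fail all three: the joint set and the DHPG-only set coincide, and the rule costs nothing.

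**The case against.** The strongest reply is that the text need not be read this way. The outcomes bullet refers to criteria for determining pharmacodynamic parameters and does not name the pharmacodynamic population. The parameters tabulated in section 20.1 (k_in, k_out, I_max, IC50, E_max, EC50) come from DHPG or metabolite concentrations and need no eye tracking. The DHPG model itself has no pupil input. Pupillometry is repeated at four research visits with practice trials, so one poor session need not make a child's data inadequate. Section 16.2 keeps all collected data for analysis, and section 20.2 says weighting or imputation will be considered.

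Part of this stands. A reader might infer that a child who fails one measure is lost from every pharmacodynamic and clinical-outcome analysis. The documents do not support that: the restriction is on the PD-linked outcomes analysis, and no sentence expressly bars a child with DHPG data from the DHPG test. But saving data does not say who enters which analysis, and considering imputation fixes neither a method nor a trigger. The alternative reading is possible without being stated.

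A second reply is that the 20% taken off 120 may already cover unusable data. If 20% of 120 completers lacked pupillometry and nothing else were lost, N would be 96, the number already powered. That is fair arithmetic. However, section 20.2 calls the 20% attrition and makes no separate allowance for failed markers. Section 8.2 counts the 120 by visits, so whether the margin was meant for this cannot be settled from the text.

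**Conclusion.** The point holds as a defect of definition with a modest and uncertain cost. On its plain wording, section 20.1 requires all three data types jointly. Followed literally, that removes children with complete DHPG and outcome data from the single-marker DHPG comparison.

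The size rests on an assumed failure rate. At 10% of 96, the plan's 0.6 SD benchmark is still met (81% power). At 20%, it is narrowly missed (77% power; detectable difference 0.625 SD). The loss would be larger if failures on the three measures were independent and frequent, and nil if they fell on the same children.

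A reader might go further and infer that the excluded children are the most symptomatic and that the responder comparison is therefore biased. The documents give neither a failure rate nor a link between task failure and severity. Response is also defined by percent reduction from baseline or the global improvement rating, not by absolute severity. What can be said is that the exclusion could be non-random, with direction and size unknown.

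**What to change.** In section 20.1, replace the single pharmacodynamic population with one set per marker:

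- a DHPG set, a pupillometry/eye-tracking set and a cardiovascular set, each requiring adequate data for that marker only;
- the PD-linked outcome analysis for each marker run in that marker's set, leaving the pharmacokinetic and partial-completion conditions as they are;
- the all-marker set kept only for MANOVA or other joint models.

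It would help to state, before the data are examined, what counts as adequate for each marker. Report N in every table.

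The cost is a short edit to section 20.1, with no new data collection. The downside is that N will differ between tables, so single-marker and joint results will not rest on exactly the same children, and the report must show this.
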